The study is a phase 2 clinical trial to determine the safety and efficacy of IBUD for the treatment of MA dependence. The trial will be performed at the UCLA outpatient research clinic in Hollywood, California. Treatment-seeking MA dependent volunteers will undergo screening and eligibility assessments, including determination of HIV serostatus, during a two-week placebo lead-in with a high value contingency management (CM) behavioral intervention aimed at assessing participants' ability to adhere to medication taking and initiate MA abstinence prior to the start of medication, both important predictors of subsequent treatment outcomes (Bisaga, Aharonovich et al. 2005, Anderson, Reid et al. 2009, Bisaga, Aharonovich et al. 2010). Eligible participants (N = 140) will be randomized, stratified by HIV serostatus, to IBUD (50 mg BID) or placebo (BID) treatment for 12 weeks, with twice weekly clinic visits for counseling, urine drug tests, and safety/medication adherence monitoring (Figure 4). An urn randomization procedure will be used to balance the following variables between active and placebo groups: MA use during the two-week placebo/CM lead-in period, gender, ethnicity (Hispanic versus not Hispanic), marijuana dependence, and baseline cognitive function.

Figure 4: Study Schema

The study is powered to detect a statistically significant benefit of IBUD over placebo on the primary study outcome, MA abstinence during the final two weeks of treatment (at least one of the two possible urine drug screens each week is available during weeks 11 and 12 and all available samples are MA negative, the FDA-preferred primary efficacy outcome for phase 2 stimulant trials) in the total sample (N = 140). Treatment retention for participants receiving IBUD versus placebo will also be compared.

Secondary analyses will examine medication tolerability and adverse events, as well as treatment outcomes in pre-specified subgroups defined by level of medication adherence, the ability to achieve initial MA abstinence during the placebo/CM lead-in, and baseline HIV serostatus. Exploratory analyses aimed at probing the mechanism of action for IBUD in MA dependence will examine potential associations between treatment outcomes/medication effects and a panel of inflammatory and neurotrophic markers as well as polymorphisms in dopaminergic and GDNF genes.

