Structured Clinical Interview for DSM-IV (SCID) (Spitzer, Williams et al. 1995): Participants must meet DSM-IV criteria for methamphetamine dependence, as determined by the SCID during screening. A full SCID, as well as the Antisocial Personality Disorder (ASPD) subsection of the SCID-II will be completed by a study clinician (following training on the instrument) These results will be used to estimate the extent of co-morbid psychiatric diagnoses, and to verify that the participant does not have an active psychiatric disorder that precludes safe study participation.

Timeline Follow-Back method (TLFB) (Sobell, Sobell et al. 1986) will be used to determine days of use and quantities of use of cigarettes, alcohol, and other drugs over a 30-day period prior to screening. The same method anchored in the past 7 days will be used weekly during the second week of screening and during the medication and follow up phases.

Urinary Cotinine: Cigarette smoking status will be monitored biologically weekly via measurement of urinary cotinine.

Urine Drug Screening for benzodiazepines, marijuana, opiates, cocaine, and MA will be monitored using an onsite qualitative urine test device. Subjects will be warned that tampering with samples and taking OTCs that cross-react with the MA panel will be interpreted as positive for illicit substance use with consequences of being dropped from study participation. Urine drug screening will be completed at *each* study visit. If a participant is unable to attend a clinic visit (e.g. out of town, holiday, etc.), subjects may provide drug screening samples using oral test kits.

Urinary Riboflavin concentration will be measured on each urine specimen via fluorimetry using a Quantifluor Fluorometer (Promega Corp). Urinary riboflavin ≥ 900 ng/ml will be considered positive for active pill taking.

Vital Signs: Blood pressure, pulse, respiration rate, and temperature will be collected at each study visit.

Wender Utah Rating Scale (WURS) (Wender, 1995), administered during screening, retrospectively assesses ADHD-relevant childhood behaviors and symptoms in adults consisting of 25 items. Estimates of ADHD in the population of MA abusers are between 15%-35%.

Assessment of Neurocognitive Endophenotypes Implicated in MA Dependence

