During weeks 4 and 13, participants will repeat the following tasks: Montreal Cognitive Assessment; MATRICS CPT-II; HVLIT-R; BVMT-R; SST; TMT; DDT; WAIS-IV Letter Number Sequencing ; WAIS-IV Symbol Search, WAIS-IV Digit Symbol Coding; N-Back Task; DKEFS Color Word Interference and the Iowa Gambling Task.

Data Analysis: The primary objective of this study is to determine the efficacy of IBUD as a treatment for MA dependence and to provide FDA with sufficient data to advise whether IBUD should move forward for marketing as a MA dependence treatment. The primary outcome variable is the FDA-specified criterion of significant MA abstinence at the end of treatment defined as no self-reported MA use during the final two weeks of treatment (weeks 11/12) confirmed via urine drug screens (at least one of the two possible urine specimens each week is available during weeks 11 and 12 and all available urine specimens are MA-negative). The study is powered to detect a significant difference in the proportion of participants achieving this outcome in the IBUD versus placebo groups. Additional measures of clinically meaningful reductions in MA use during treatment will also be assessed in the event that IBUD produces effects on MA use that do not meet the abstinent at end of treatment threshold. In addition to MA use outcomes, treatment retention, an important clinical variable that is associated with long-term treatment outcomes in substance abuse treatment (Hser, Evans et al. 2004), with IBUD versus placebo will be compared. Effects of potential confounders on each of these outcomes will also be examined including: (1) medication non-adherence, (2) medication safety and tolerability (adverse event rates), and (3) ability to achieve initial MA abstinence with the CM intervention during the two week lead-in period.

A general univariate strategy will be used to test for differences between conditions at baseline and along all outcome variables using bivariate analyses (i.e., t-tests/ANOVA for continuous variables; χ^2 for dichotomous variables). A multivariate analysis will also be used when appropriate to control for co-variables known to influence MA dependence treatment outcomes including age, gender, baseline severity of MA dependence, HIV status, and ability to achieve initial abstinence during the CM lead-in.

Aim 1: To determine whether IBUD reduces MA use more than placebo among MA dependent participants.

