Hypothesis 1: IBUD will result in significantly greater reductions in MA use than placebo

Analysis: The outcome of reductions in MA use will be assessed using results from twice weekly urine drug screens for MA-metabolites and self-reported MA use (weekly time line follow-back). This analysis is an intent-to-treat analysis that involves the period from Day 0 to the end of the 12 week active medication period. Univariate composites of urine drug screen results include:

- FDA-Specified Criterion of significant abstinence – two weeks continuous MA abstinence at end of treatment (primary study outcome): The proportion of participants in the IBUD and placebo groups with two weeks continuous MA abstinence during weeks 11 and 12, defined as self-reported MA abstinence confirmed by urine drug screens (at least one of the two possible urine specimens possible each week is available and all available are MA-negative) during weeks 11 and 12.
- Treatment Effectiveness Score: mean number of MA-free urine specimens provided during the 12 week outpatient treatment period in the IBUD versus placebo groups.
- Joint Probability Index: Measures whether an average participant is retained and abstinent at a given point in the trial. The probability that a participant is retained at a given point is multiplied by

the probability a participant is abstinent at the same point. The measure will be calculated at the midpoint (end week 6) and termination (end week 12) for IBUD and placebo groups.

A logistic regression model will be used to compare the odds of the dichotomous outcome variable two weeks continuous MA abstinence at end of treatment for IBUD versus placebo groups, controlling for important co-variables including age, gender, severity of baseline MA dependence (number of MA use days in the past 30 days at baseline), and HIV status. Longitudinal modeling techniques including GEE will be then used to model MA use as measured via urine drug screen results and self-report of drug use, taking advantage of the twice-weekly urine specimens collected during the trial. Additional covariates such as gender, age, baseline MA use may be included as appropriate.

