APPENDIX II: Assessment Schedule for Ibudilast Phase 2 Trial

STUDY ASSESSMENT TABLE FOR IBUDILAST PHASE II TRIAL

Measures	Baseline	Medication Phase			Follow-Up
		Weekly Wks 1-12	Specific time	Monthly Wk 4, 8, 12	
	0.6 visits				Weekly Wk 13, 14, 15, 16
Clinical measures					
Medical history	X				
Physical	X				wk 13
EKG	X		wks 3, 8		wk 13
Labs	X		wks 3, 8		wk 13
HCV serology	X				wk 13
HIV test	X				wk 13
if HIV+, CD4/viral load	X				wks 13, 16
DNA/SNP sample	X				
Inf/NT markers (serum and plasma)	X		wks 3, 8		wk 13
Pregnancy test	X			X	
Adverse events	X	X			X
Urine drug screen	e	e			X
Vital signs	e	e			X
Progress note	e	e			X
Urinary cotinine	X	X			X
Concomitant medications	X	X			
Pill count		X			wk 13
HIV medication adherence	X			X	wk 16
Medication compliance (urine) via UV fluorimetry	e	e			wk 13
Stored urine aliquot	X	e			
Medication compliance (serum)			wk 3		
Behavioral assessments					
ASI	X				
BIS-11	X				
PSS-14	X				
ELSQ			wk 3		
PLC-C			wk 3		
SCID	X				
WURS	X				
HRBS	X			X	wk 16
BSI	X			X	wk 16
MA Craving VAS	X	X			X
C-SSRS	X	X			X
HAMD	X	X			X
TLFB	X (0.1, 0.4)	X			X
Medical Management Counseling	X	X			
Cognitive functioning measures After July 2016, only MOCA is still being administered					
WTAR	X				
WRAT4	X				
MOCA	X (0.1)		wk 4		wk 13
BVMT-R	X		wk 4		wk 13
HVLT-R	X		wk 4		wk 13
CPT-II (MATRICS version)	X		wk 4		wk 13
CPT-II (Connors' version)			wks 2, 6, 10		
TMT	X		wk 4		wk 13
SST (comp)	X		wk 4		wk 13
DDT (comp)	X		wk 4		wk 13
Iowa Gambling Task	X		wk 4		wk 13
Symbol Coding (WAIS-IV)	X		wk 4		wk 13
Symbol Search (WAIS-IV)	X		wk 4		wk 13
Letter Number Sequencing (WAIS-IV)	X		wk 4		wk 13
N-Back Task	X		wk 4		wk 13
DKEFS Color Word Interference	X		wk 4		wk 13
Pursuit Rotor Task	X		wk 4		wk 13

e: every visit.

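### The weekly TLFB's fixed 7-day look-back leaves days of weeks 11-12 unasked when interviews are more than 7 days apart or one is missed, and the plan does not say that the week-13 TLFB counts

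*Combined protocol and SAP*

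**What the plan says.** All references are to the combined protocol and SAP.

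- **Instrument.** Under Study Measures and Assessments, the TLFB covers 30 days at screening. After that, "The same method anchored in the past 7 days will be used weekly". The timing is "weekly during the second week of screening and during the medication and follow up phases".
- **Schedule.** Appendix II marks the TLFB weekly in weeks 1-12 and again in the follow-up column, headed "Weekly Wk 13, 14, 15, 16". No section fixes the weekday of the interview or sets a minimum or maximum interval between interviews.
- **Outcome.** Data Analysis defines success as "no self-reported MA use during the final two weeks of treatment (weeks 11/12) confirmed via urine drug screens". Aim 1 repeats it as two weeks of continuous abstinence, "defined as self-reported MA abstinence confirmed by urine drug screens", and gives the source of self-report as "self-reported MA use (weekly time line follow-back". At least one of two urine specimens must be available in each of weeks 11 and 12, and all available specimens must be negative.
- **Analysis period.** Aim 1 states: "This analysis is an intent-to-treat analysis that involves the period from Day 0 to the end of the 12 week active medication period".
- **Missing data.** Power calculations treats participants who do not complete the trial, and so lack urine-confirmed abstinence, as non-abstinent. No rule covers a participant who meets the urine requirement but has days that no interview asked about.

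**The concern.** The outcome is a statement about 14 consecutive days, while the instrument asks about 7 days counted back from whenever the interview happens. The two fit together only if interviews are never more than 7 days apart and one takes place after week 12 ends. The plan schedules such an interview but ties it to nothing, and the Aim 1 sentence that ends the analysis at week 12 could lead an analyst to leave it out.

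At stake is the classification of a binary primary endpoint. A participant could use MA on a day that falls between two windows, give negative specimens at the visits attended, truthfully answer every question put, and be counted as continuously abstinent. If such errors occurred at similar rates in both arms, they would tend to shrink a real difference.

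**Working it through.** The plan gives no figure for days covered, so there is none to reproduce. The check is a count.

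**Inputs.** Weeks 11-12 are days 71-84 (10 × 7 + 1 to 12 × 7), and week 13 is days 85-91. Let the interviews fall on day *d* of week 11, day *e* of week 12 and day *f* of week 13, each from 1 to 7. The look-back is 7 days. The plan does not say whether the interview day itself counts. The examples below exclude it, so an interview on day *t* covers *t* − 7 to *t* − 1.

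**All three interviews done and used.** The interval from week 11 to week 12 is 7 + (*e* − *d*), so max(0, *e* − *d*) days are missed. Likewise max(0, *f* − *e*) days are missed between weeks 12 and 13. In total:

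unasked days = max(0, *e* − *d*) + max(0, *f* − *e*)

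The maximum is (*e* − 1) + (7 − *e*) = 6. Counting the interview day moves each gap by one day but does not change its length.

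- *Same weekday, for example days 74, 81, 88.* Coverage is 67-73, 74-80 and 81-87. Unasked: 0 of 14.
- *Days 71, 84, 91.* Coverage is 64-70, 77-83 and 84-90. Unasked: days 71-76, which is 6.
- *Milder drift, assuming clinic visits on days 1 and 4 of each week and the TLFB at either one.* For days 71, 81, 85, coverage is 64-70, 74-80 and 78-84. Unasked: days 71-73, which is 3. Of the 2 × 2 × 2 = 8 patterns, 4 leave a 3-day gap and 4 leave none.

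**Week-12 TLFB missed, weekday unchanged.** Interviews are 14 days apart, so 14 − 7 = 7 days are unasked. With days 74 and 88, these are days 74-80. This matters for the primary outcome only if the participant still gave a week-12 urine, because a week without one already fails the definition.

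**Week-11 TLFB missed.** The week-12 window starts too late to reach all of week 11. Unasked: *e* − 1 days, so 0 to 6 (1 to 7 if the interview day counts).

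**Week-13 TLFB not used.** Every day from the week-12 interview day to day 84 is unasked (if the interview day counts, every day after it). No look-back length changes this, because those days have not yet happened when the interview takes place.

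**After the fix.** With recall running back to the previous completed interview, intervals join without gaps. Once a TLFB has been completed after day 84 and is counted, 0 of the 14 days are unasked for every placement above.

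**The case against.** The strongest reply is that the plan already contains the remedy. The TLFB continues weekly in follow-up, Termination and Follow-Up Procedures asks completers back in week 13, and at regular spacing nothing is missed. This stands as far as it goes, but the plan neither requires regular spacing nor says the week-13 report counts.

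Self-report is also not the only safeguard. Urine is collected at each of two weekly visits, and any available positive fails the outcome. That is up to four specimens over the two weeks, with two as the minimum, and the higher visit payment in weeks 11-12 supports attendance. Weekly counseling includes a brief review of drug use, and the drop-out tracking section aims to collect weekly data even from people who stop attending. These points limit the exposure. They do not close it, since the counseling review is not named as a source for the outcome.

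The Research Plan also words the primary outcome by urine alone ("all available samples are MA negative, the FDA-preferred primary efficacy outcome for phase 2 stimulant trials"). Under that wording the TLFB would not touch the primary endpoint. Data Analysis and Aim 1 both include self-report, so the definitions need reconciling.

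Three stronger readings are tempting, and the documents do not support them:

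- *That the 7-day look-back leaves 1 to 7 days uncovered for everyone.* That count uses only the week-11 and week-12 interviews and excludes the interview day (0 to 6 if it counts). With interviews 7 days apart, all those days fall on or after the week-12 interview day, and a 14-day look-back would leave the same ones uncovered.
- *That about three quarters of participants have a gap.* Of the 7 × 7 × 7 = 343 placements, 84 leave no gap, so 259 (76%) do. This treats interview days as independent and uniform over the week. The plan describes no such pattern, so 76% is not a forecast.
- *That the lead-in is compromised because Appendix II places the TLFB at visits 0.1 and 0.4 only.* The urn variable and the contingency payments for that week rest on urine, and the baseline-use covariate is the past 30 days. The gap feeds no specified stratifier, covariate or endpoint.

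**Conclusion.** The point holds as a mismatch between a 14-day outcome and a fixed 7-day instrument, and it is conditional. With exact 7-day spacing and the week-13 TLFB used, there is no gap. Otherwise up to 6 days are unasked with all three interviews done, and 7 if the week-12 TLFB is missed and the weekday is unchanged. These two figures do not depend on whether the interview day counts. They do assume that the definition in Data Analysis and Aim 1 governs and that the week-13 report is used.

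A reader might go further and infer a known number of false successes or a known loss of power. The documents do not allow that. They give no interview dates, no rate of missed TLFBs, no detection window for the urine screen and no rule that scores an unasked day as abstinent. The misclassification is possible, its size cannot be derived, and twice-weekly urine limits it. This is a cheap improvement worth making, not a defect that invalidates the primary analysis.

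**What to change.** Two sentences would do it.

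1. In the TLFB entry, for the medication and follow-up phases, replace the past-7-days anchor with every day since the last completed TLFB.
2. In the outcome definition, state that any MA use reported for days 71-84 at any later TLFB, including the week-13 one, counts as non-abstinence.

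Both have precedent in the plan: the pill-count entry already asks about the period since the last visit, and the screening TLFB already covers 30 days. The cost is slightly longer recall and a few more interview minutes when visits are spaced out or missed. Participants seen every 7 days notice no change.

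One case remains. If no follow-up TLFB is ever completed, the days after the last in-treatment interview stay unasked, and the outcome definition should say how they are scored.
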